### 4.5 Special Subpopulations

BMI change will be tabulated by age and gender. Additionally, further exploratory subgroup analyses of the primary efficacy endpoints may include evaluation by race and/or other subgroups deemed medically and/or scientifically important.

## 5. DATA Handling

### 5.1 Time Points and Visit Windows

Day 0 (Visit 2) is defined as the Baseline/Randomization visit, is also the first day of treatment. Relative days are calculated as (assessment date – Day 1 date). The day prior to Day 0 is Day -1.

The following visit windows defined in Table 1 will be used for the by-visit analyses of the primary endpoint, the secondary and other endpoints. All other analyses will use the nominal study visit as defined in the Study Schedule and eCRF.

If there are multiple visits (scheduled or unscheduled) within a visit window, the measurement closest to the target day of the visit will be used in the analysis. If the measurements are equally distant to the target day, then the later one will be used in the analysis. If both scheduled and unscheduled visits fall within the same visit window, the scheduled visit will be used for analysis.

**Table 1 Definition of Visit Windows**

Visit	Visit time (Week)	Acceptable visit window	Study Day Analysis Visit Window Range
1 Screening	Screening	-28 days from baseline	NA
2 Baseline a	Week 0	±3 days	Day -27 to Day 2
3 Treatment	Week 4	±1 week	Day 3 to Day 41(Week 6)
4 Treatment	Week 8	±1 week	Day 42 to Day 69(Week 10)
5 Treatment	Week 12	±1 week	Day 70 to Day 97(Week 14)
6 Treatment	Week 16	±1 week	Day 98 to Day 125(Week 18)
7 Treatment	Week 20	±1 week	Day 126 to Day 153(Week 22)
8 Treatment	Week 24	±1 week	Day 154 to Day 181(Week 26)
9 Treatment	Week 28	±1 week	Day 182 to Day 209(Week 30)
10 Treatment	Week 32	±1 week	Day 210 to Day 237(Week 34)
11 Treatment	Week 36	±1 week	Day 238 to Day 265(Week 38)
12 Treatment	Week 40	±1 week	Day 266 to Day 293(Week 42)
13 Treatment	Week 44	±1 week	Day 294 to Day 321(Week 46)
14 Treatment	Week 48	±1 week	Day 322 to Day 349(Week 50)
15 Treatment	Week 52	±1 week	Day 350 to Day 377(Week 54)
16 End of Study/ET b	Week 56/ET	±1 week	Day 378 to Day 398(Week 57)

a Baseline Visit (Visit 2) can be scheduled up to 4 weeks from Screening.

b. ET = Early Termination

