9.2 Study Period

The study period for each subject will begin when written informed consent is provided and will continue until Week 56 or early termination is completed. Sites should link the scheduling of visits to the baseline/randomization visit (Visit 2, Day 0). Visit windows are provided to allow subject and site scheduling convenience. However, every effort should be made to ensure that visits occur within these windows so that the overall treatment duration is 56 weeks for subjects

who complete all visits. In certain instances, adverse event information may be required for events occurring after the study period (Section 11.3).

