APPENDIX 1: SCHEDULE OF EVENTS

	Screening	Baseline ^a (+ 3 days)	Treatment (± 1 Week)														
			0	4	8	12	16	20	24	28	32	36	40	44	48	52	56/ET
Study Weeks→	Screen	1	2	3	4	5	6	7	8	9	10	11	12	13	14	15	16
Informed Consent/Accent	X																
Demographics and Medical History	X																
Review Inclusion/Exclusion	X	X															
Weight, Waist Circumference, Height, and BMI	X	X	X	X	X	X	X	X	X	X	X	X	X	X	X	X	
Physical Exam (include Tanner Staging)		X														X	
Concomitant Medication	X	X	X	X	X	X	X	X	X	X	X	X	X	X	X	X	
Vital Signs	X	X	X	X	X	X	X	X	X	X	X	X	X	X	X	X	
Adverse Events		X	X	X	X	X	X	X	X	X	X	X	X	X	X	X	
PHQ-9/C-SSRS	X	X	X	X	X	X	X	X	X	X	X	X	X	X	X	X	
Electrocardiogram		X														X	
DXA (selected sites only)		X														X	
Chemistry (Fasting)	X		X	X						X						X	
Hematology/Lipids	X									X						X	
TSH, HIV, HCV, HBsAg	X																
HbA1c	X					X						X				X	
Urinalysis	X															X	
Urine Drug Screen	X																
Urine Pregnancy Test	X	X	X	X	X	X	X	X	X	X	X	X	X	X	X	X	
Hand and Wrist X-ray (bone age assessment)		X														X	
OGTT ^b		X														X	
Cognitive Battery (CANTAB)	X ^c	X			X											X	
IWQOL-Kids		X														X	
Diet/Lifestyle Counseling		X	X	X	X	X	X	X	X	X	X	X	X	X	X	X	
Contraception/Pregnancy Counseling	X	X	X	X	X	X	X	X	X	X	X	X	X	X	X	X	
Randomization		X															
Dispense Study Drug		X	X	X	X	X	X	X	X	X	X	X	X	X	X	X	
Drug Accountability			X	X	X	X	X	X	X	X	X	X	X	X	X	X	
Schedule Next Visit	X	X	X	X	X	X	X	X	X	X	X	X	X	X	X	X	

^a Baseline can occur up to 4 weeks from Screening.^b Blood sample at 2 hours post glucose load^c Familiarization session only

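### The Week 56 analysis window in SAP Table 1 ends at Day 398, one day short of its own ±1 week limit (Day 399), and the relative-day formula beside it uses an undefined Day 1 date

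*SAP*

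**What the plan says.** Both documents put the origin of the day count at baseline. SAP 5.1 states that "Day 0 (Visit 2) is defined as the Baseline/Randomization visit", adds that this is the first day of treatment, and calls the day before it Day -1. Protocol 9.2 agrees: "Sites should link the scheduling of visits to the baseline/randomization visit (Visit 2, Day 0".

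The next sentence of SAP 5.1 gives the formula: "Relative days are calculated as (assessment date – Day 1 date". The section does not define Day 1.

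On-time attendance is set at ±1 week. Protocol Appendix 1 heads the post-baseline columns "Treatment (± 1 Week", and SAP Table 1 repeats ±1 week in its acceptable-window column for every post-baseline row, including Week 56/ET.

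For analysis, Table 1 gives Week 52 as "Day 350 to Day 377(Week 54" and Week 56 as "Day 378 to Day 398(Week 57". Week 56 is the last row. SAP 5.1 says that these windows "will be used for the by-visit analyses of the primary endpoint, the secondary and other endpoints"; the nominal visit is used only for other analyses.

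**The concern.** The analysis window for the primary time point is narrower, at its late end, than the visit window printed beside it. A subject who attends the final visit seven days after target is on time for the site but has no row in the table that decides which measurements count at Week 56. The tie-break rules in SAP 5.1 choose among measurements inside a window and do not rescue one that lies outside all of them. The fallback to nominal visits does not help either, because the primary endpoint is expressly windowed.

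What is at stake is an observed, on-protocol BMI at the primary time point, and the secondary endpoints measured at the same visit. The loosely worded day formula adds to this: two programmers following the text could differ on whether the same measurement is in or out.

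**Working it through.** **Inputs.** Baseline = Day 0 (SAP 5.1, Protocol 9.2). Visit window = target ±7 days (Protocol Appendix 1, SAP Table 1). Analysis windows as printed in SAP Table 1.

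**Step 1: reproduce the printed figure.** Every post-baseline upper bound equals 7 × (week in brackets) − 1:

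- Week 4 row: 7 × 6 − 1 = 41
- Week 52 row: 7 × 54 − 1 = 377
- Week 56 row: 7 × 57 − 1 = 398

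All 14 rows follow this rule, so Day 398 is consistent with the rest of the column.

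**Step 2: compare with the visit window.** Target = 7 × week; on-time range = target − 7 to target + 7.

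| Visit | Target day | On-time days | Analysis window | Upper bound − target | On-time days all inside? |
|---|---|---|---|---|---|
| Week 4 | 28 | 21–35 | 3–41 | 13 | Yes |
| Week 8 | 56 | 49–63 | 42–69 | 13 | Yes |
| Week 52 | 364 | 357–371 | 350–377 | 13 | Yes |
| Week 56 | 392 | 385–399 | 378–398 | 6 | No (Day 399) |

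The rows for Weeks 12 to 48 behave like Week 8. In the first 13 rows, the day after the upper bound (42, 70, …, 378) opens the next row, so no day is lost. After Week 56 there is no next row.

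**Step 3: count.** 14 rows × 15 on-time days = 210. Of these, 209 fall in their own row and one, Day 399, falls in none. The baseline row is not counted. It allows ±3 days and ends at Day 2, but Day 3 falls in the Week 4 row and so is not left unassigned.

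**Step 4: the day formula.** Take a visit 399 calendar days after baseline.

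- If Day 1 means the first-treatment date, it is the same date as Day 0. Relative day = 399, outside 378–398.
- If Day 1 means the day after baseline, relative day = 399 − 1 = 398, inside. But baseline becomes 0 − 1 = −1, against the SAP's own definition of Day 0.

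Among the 210 on-time days, Day 399 is the only one whose row depends on this reading. Off-schedule days on a boundary also depend on it: Day 3 and the 13 internal boundaries 42, 70, …, 378. For example, Day 378 is in Week 56 under the first reading and in Week 52 (as 377) under the second.

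**The case against.** **Analysis windows need not match visit windows.** This is true, and 13 rows are wider than their visit windows without harm. Only Week 56 is narrower at one end, and the SAP gives no reason. Protocol 9.2 asks that "every effort should be made to ensure that visits occur within these windows"; a Day 399 visit meets that request.

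**The Day 1 wording may be harmless.** SAP 5.1 makes Day 0 the first day of treatment, so Day 1 date may simply mean the first-treatment date. This largely stands. A reader might infer that the two sentences of SAP 5.1 flatly contradict each other about the Day 399 visit. They do so only if Day 1 is the day after baseline, and that reading conflicts with the SAP's own Day 0. What remains is an undefined term that needs replacing.

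**Nothing says that the value would be imputed.** This also stands. A reader might infer that a Day 399 BMI would be replaced by an imputed value. SAP 5.2 and 6.6.1 direct the retrieved-dropout imputation, for which washout is the fallback, at subjects who leave the study prematurely. A completer seen on Day 399 is not one of them. If that value were simply left out, the repeated-measures model would use the subject's other visits without substituting a value. Exclusion from Week 56 is a fair reading of the table; the handling afterwards is unstated.

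**The point does not extend to late returns or early-termination values.** Protocol 7.3 and 9.1.4 ask withdrawn subjects back around Week 56, so a reader might see a wider missing-data problem. Table 1 is a closed set of study-day ranges and already settles where such values fall.

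**The cause is not established.** The bracketed weeks may be an end-of-row convention carried into the last row, or may name the week that contains the upper bound. Both fit all 14 rows. The one-day gap exists either way.

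**Conclusion.** The inconsistency is real and minor. With baseline as Day 0 and the ±1 week window read as inclusive, the Week 56 analysis window is one day too short, and an on-time visit on Day 399 is unassigned in the by-visit analysis of the primary endpoint. The undefined Day 1 date leaves the same visit open to two treatments, one of which breaks the SAP's definition of baseline.

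The effect is confined to one on-time day in 210. How many subjects attend on that day cannot be worked out, because the documents give no distribution of visit dates. No effect on power, the treatment estimate or the trial's conclusion is shown, and none should be inferred. The point matters because it concerns which observed values count at the primary time point, and such a rule should be unambiguous before treatment codes are known.

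**What to change.** Make two edits together in SAP 5.1 before unblinding:

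1. In Table 1, change the Week 56 row to run from Day 378 to Day 399.
2. In the relative-day formula, replace the Day 1 date with the Day 0 (baseline/randomization) date.

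Visits and data collection do not change. If days are already counted from Day 0, the edits have no downside: they only keep values from Day 399, which the protocol already treats as on time. If days had been counted from the day after baseline, the second edit would also move off-schedule or unscheduled visits that fall exactly on a window boundary by one row. The programming team should therefore confirm which origin is in use when making the change.

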## 5.2 Handling of Dropouts, Missing Data, and Outliers

For subjects who discontinue treatment prior to study completion, every attempt will be made to have them continue with clinic visits and study assessments. Particular attention will be given to collecting Week 56 assessments of weight and height, regardless of when subjects discontinued treatment.

Missing data will not be imputed for safety analyses. The safety evaluations will be performed on observed data only.

For the MMRM (mixed effects model with repeated measures) method used for the primary analysis on the primary endpoint, the retrieved dropouts will be used to impute missing data for subjects who discontinue the study prematurely. If there are no sufficient retrieved dropouts, then the wash-out imputation method will be applied.

The following sensitivity analyses will be considered to explore the impact of missing data on the conclusion of the primary analysis.

The first sensitivity analysis is using a multiple imputation method based on the monotonic missing pattern under the assumption of missing at random (MAR). The intermittent missing data will be imputed using multiple imputation MCMC (Markov chain Monte Carlo) procedure.

The second sensitivity analysis is also using multiple imputation, however, under the assumption of missing not at random (MNAR) to explore the validity of MAR using pattern-mixture model:

- 1) For subjects who discontinue study participation prior to Week 56 and do not have follow-up visit, the missing data will be imputed using the observed data from the subjects in the same arm who discontinue the study treatment but have the primary endpoint measurement in the follow up visit using a regression method. The intermittent missing data will be imputed using multiple imputation MCMC procedure. An ANCOVA (analysis of covariance) model using a similar mixed procedure (without the repeated measures) as the primary analysis will be applied to these multiple-imputed % change in BMI at Week 56 with treatment, baseline BMI value as a covariate, and age and gender as stratification factors. The results of ANCOVA analysis on the multiple imputed datasets will be combined and summarized.
- 2) Tipping point analyses: Subjects from the treatment arm who drop out the study will have their unobserved efficacy data imputed by the observed data from completers in the same arm using the multiple imputation method based on the monotonic missing pattern under the assumption of MAR with the resulting imputed values further worsened by an amount  $\delta$ . Subjects who drop out the study from the control arm will be assumed to exhibit the same evolution of the disease as the completers in control arms and their values will be imputed by the multiple imputation method based on the monotonic missing pattern under the assumption of MAR above without the addition of  $\delta$ . Sensitivity analysis may be performed for a range of  $\delta$  to find a “tipping point” value of  $\delta$  at which study conclusions start to change. When  $\delta=0$  the missing data are assumed to be MAR. When  $\delta > 0$ , the missing data are assumed to be MNAR.

The third sensitivity analysis is the last observation carried forward (LOCF). For those subjects who discontinue study participation prior to Week 56, the last observed weight and height will be used to derive the change in BMI.

Similar analyses will be performed for the primary endpoint for the mITT population.

## 6. Statistical Methods

### 6.1 General Principles

All data processing, summarization and analyses will be performed using SAS Environment / Version 9.3 (or later) of the SAS® statistical software package.

The following principles will be applied to all TFLs unless otherwise stated:

Principle	Value
Significant tests	Two-sided and use a 5% significance level.
Treatment group labels and order presented	Placebo VI-0521 Mid VI-0521 Top
Tables	Data in summary tables presented by treatment group, assessment and visit (where applicable).
Listings	All data collected presented by treatment group, site, subject, and visit (where applicable), unless otherwise specified.
Descriptive summary statistics for continuous variables	Number of observations (N), mean, standard deviation (SD), minimum, median and maximum.
Descriptive summary statistics for categorical variables	Frequency counts and percentages [n (%)].
Denominator for percentages	Number of subjects in the pertinent analysis population, unless stated otherwise in table shells.
Include "Missing" as category	Demographics and Other Baseline Characteristics only
Display for 0 percentages	Blank
Display to one more decimal place than collected value	Mean Median Minimum Maximum
Display to two more decimal places than collected value	Standard Deviation Confidence Interval
Limit of precision for displays	3 decimal places
Date Format	DDMMYYYY

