**Figure 1. Schematic Diagram of Study Design**

## 2.3 Sample Size and Power

In previous studies in adults, VI-0521 mid-dose (PHEN/TPM 7.5 mg/46 mg) resulted in a placebo-subtracted BMI reduction of 2.4 units with a standard error approximately 0.16 units and a within treatment standard deviation of 2.9. A very conservative estimate of the treatment difference between the mid-dose and placebo would be 2 units of BMI which represents more than 2 standard errors below what was observed before. If we enroll 200 subjects (50 placebo, 50 mid-dose, and 100 top-dose), we will have at least 90% power to detect a statistically significant difference between the top-dose (PHEN/TPM 15 mg/92 mg) and the placebo because we could assume that the top-dose will have a higher effect size than the mid-dose. This calculation assumes that there will be an approximately 30% dropout rate. This sample size will also provide approximately 80% power to detect a statistically significant difference between the mid-dose and placebo.

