### **4.2 Safety**

This population will be comprised of all subjects who were initially randomized and received at least one dose of study drug. This will be the primary population for all summaries of subject disposition and baseline characteristics, and safety analyses for purposes of regulatory submissions. The safety population is based on the treatments actually received.

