### 6.7.3 C-SSRS

For each item of the C-SSRS, counts and percentages will be presented by treatment group and in total summarizing the number of yes responses at each study visit. In addition, a composite measure will be summarized at each study visit that includes the following C-SSRS items: Active suicidal ideation with some intent to act without specific plan, Active suicidal ideal with specific plan and intent, Actual attempt, Engaged in non-suicidal non-injurious behavior, Interrupted attempt, Aborted attempt, Preparatory acts or behavior, and Suicidal behavior. The baseline distribution of responses to the C-SSRS will also be presented.

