### 6.7.7 Laboratory Evaluations

A summary of observed values and change from baseline will be presented for all laboratory parameters with numerical measures using descriptive statistics. Shift tables displaying low-normal-high at baseline versus low-normal-high at end of study in a 3-by-3 contingency table will be provided. For selected laboratory parameters, scatter plots of baseline versus Week 56 results, will be produced by treatment group.

A laboratory value that is above or below normal range will be considered an abnormal value. For selected laboratory parameters, threshold limits of clinical concern will be defined as multiplicative factors of the normal ranges. The list of multiplicative factors for each laboratory parameter will be included in the Statistical Analysis Plan. The frequency and percentage of subjects with laboratory results above or below the normal range and threshold limits at each scheduled assessment or any time during the treatment will be summarized by treatment group.

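### By default the SAP divides by-visit C-SSRS and laboratory-abnormality percentages by the whole Safety population, so unassessed subjects count as non-cases, at odds with its own observed-data rule

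*SAP*

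**What the plan says.** The table of principles in SAP 6.1 opens with "The following principles will be applied to all TFLs unless otherwise stated". Its denominator row reads "Number of subjects in the pertinent analysis population, unless stated otherwise in table shells", and its row on including a missing category reads "Demographics and Other Baseline Characteristics only".

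The population for safety tables is defined in SAP 4.2: "This population will be comprised of all subjects who were initially randomized and received at least one dose of study drug". No post-baseline assessment is needed to belong to it.

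Two sections plan percentages by visit:

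- SAP 6.7.3, for each C-SSRS item: "counts and percentages will be presented by treatment group and in total summarizing the number of yes responses at each study visit". A composite is also summarised at each visit.
- SAP 6.7.7, for laboratory results: the frequency and percentage of subjects "above or below the normal range and threshold limits at each scheduled assessment or any time during the treatment".

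Neither section names a denominator. SAP 5.2 rules out imputation for safety analyses and adds: "The safety evaluations will be performed on observed data only".

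On expected loss, SAP 2.3 says of the power calculation: "This calculation assumes that there will be an approximately 30% dropout rate". The protocol synopsis calls the same 30% a worst case.

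**The concern.** Under the written default, a subject with no C-SSRS or no laboratory sample at a visit cannot appear in the numerator, remains in the denominator, and appears in no missing row. The arithmetic is the same as scoring that subject no or normal. By-visit rates would then drift down as subjects leave, whatever happens to those who stay. An arm that loses more subjects would look safer.

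Safety is a primary objective, and these tables cover suicidal ideation and behaviour in adolescents. Leaving may itself be related to mood: Protocol 8.5.1 requires discontinuation from the study for subjects who come to need certain psychiatric medicines, among them tricyclic antidepressants and lithium.

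**Working it through.** **Inputs**

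- Arm sizes 50 placebo, 50 mid-dose, 100 top-dose (SAP 2.3).
- Planning dropout 30% (SAP 2.3; worst case in the protocol synopsis).
- m = share of the Safety population with no assessment counted at a given visit. The documents give no figure, so a range is used.
- p = rate among assessed subjects, set at 10% for illustration. The relative results do not depend on p.

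**1. The plan's own use of 30%.** The documents state no figure for the denominator effect. The only stated results that use the 30% are the powers. Take a two-sample t comparison, two-sided alpha 0.05, difference 2 BMI units, SD 2.9.

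- Mid-dose against placebo: 50 × 0.70 = 35 per arm; power 0.812 (stated: about 80%).
- Top-dose against placebo: 100 × 0.70 = 70 against 35; power 0.910 (stated: at least 90%).

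Both reproduce. The 30% is therefore an allowance for lost BMI outcomes, not a forecast of missing safety assessments.

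**2. Formula.** Assessed subjects = N(1 − m). Cases = p × N(1 − m). Displayed percentage = cases / N = p(1 − m). Relative understatement = [p − p(1 − m)] / p = m.

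**3. Numbers for the top-dose arm, N = 100, p = 10%**

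| m | Assessed | Expected cases | Shown with N | Relative understatement |
|---|---|---|---|---|
| 5% | 95 | 9.5 | 9.5% | 5% |
| 10% | 90 | 9 | 9% | 10% |
| 20% | 80 | 8 | 8% | 20% |
| 30% | 70 | 7 | 7% | 30% |

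With the number assessed as denominator, the last row is 7/70 = 10% and the understatement is zero.

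**4. Where m is likely to lie**

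- *Laboratory data.* SAP 6.7.7 assigns samples to visits by study day, and SAP Table 1 sets the Week 56 window at Day 378 to Day 398. An early-termination sample usually falls in an earlier window, so m at Week 56 can approach the share who left and did not return.
- *C-SSRS.* SAP 5.1 uses the nominal visit for analyses outside its windowed set, and Visit 16 is labelled Week 56/ET. If C-SSRS is tabulated that way, early-termination assessments enter the last row and m there could be well below 30%. Earlier rows get no such help. If a 30% loss is assumed uniform over 56 weeks, the factor is 1 − 0.30 × 28/56 = 0.85 at Week 28 and 1 − 0.30 × 52/56 = 0.72 at Week 52.

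**5. Unequal missingness (illustration, same 10% rate in both arms)**

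- m = 10% and 20%: 0.10 × 0.90 = 9% against 0.10 × 0.80 = 8%; ratio 0.90/0.80 = 1.125.
- m = 20% and 40%: 8% against 6%; ratio 0.80/0.60 = 1.33.

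**6. The two rules side by side.** If SAP 5.2 governs, the rate is cases over subjects assessed. If SAP 6.1 governs, it is cases over N. From the same data, one programmer could print 7/70 = 10% and another 7/100 = 7%, each following the SAP. Nothing in sections 6.7.3, 6.7.7, 7 or 8 says which applies.

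**The case against.** The strongest reply is that SAP 6.1 carries its own exceptions. Its principles hold unless stated otherwise, and the denominator row defers to the table shells, which are where such detail is often set. The shells are not among the documents, so whether they already use an assessed denominator is unknown. SAP 5.2 can also be read as supplying the right rule. Even cases over N is interpretable: it is the share of the Safety population with a recorded event at that visit.

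This stands as a limit on certainty. It does not remove the point, because the only denominator rule in the SAP text is population N, and the reader of a by-visit safety percentage will take it as a rate among those assessed.

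The consequence is also bounded. These tables are descriptive and no planned test uses them. Counts accompany percentages, numeric laboratory summaries report the number of observations, disposition is shown by arm, and data are listed by subject and visit. A careful reader could rebuild the assessed number for laboratory data, less easily for C-SSRS.

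Four stronger readings are tempting but not supported:

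- *That every percentage in the SAP is affected.* The shell exception alone rules this out.
- *That Week 56 rates will be 30% too low.* Subjects who stop drug are encouraged to attend all visits, Protocol 9.1.4 has withdrawing subjects complete Visit 16 procedures, and sites also try to reach them at about Week 56.
- *That ECG and physical-examination percentages share the fault.* Both assessments are made only at baseline and end of study or early termination. SAP 6.7.10 summarises post-baseline findings rather than each visit, and SAP 6.7.9 gives yes/no categories for the investigator's assessment without stating by-visit percentages.
- *That any-time laboratory counts need a different denominator.* Population N is usual there, and no error is shown.

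**Conclusion.** The point holds for by-visit C-SSRS and laboratory-abnormality percentages, on the condition that the table shells do not override SAP 6.1. It is a stated default that biases those rates down and conflicts with SAP 5.2, not merely a missing detail.

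The relative understatement equals m exactly. The 30% upper figure requires that all of the worst-case planning dropout becomes missing assessments. That is closest to realistic for Week 56 laboratory data and less so for C-SSRS at Visit 16 if nominal visits are used. The between-arm distortion depends on missingness differing by arm. The documents give no arm-specific figures, so the examples show the mechanism only; the 40% in one of them exceeds the plan's overall worst case.

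The primary efficacy analysis is untouched. The change should be made because safety is a primary objective and the correction is nearly free.

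**What to change.** Before the tables are programmed:

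1. In SAP 6.1, add that by-visit post-baseline percentages use the number of subjects assessed at that visit, and print that number for each arm and visit.
2. In SAP 6.7.3, define assessed as having the C-SSRS administered at that visit, not as having a non-missing answer to each item. Items 3 to 5 are asked only when item 2 is positive, so an item-level denominator would shrink to those already positive and inflate the rate.
3. In SAP 6.7.7, apply the same rule per parameter within the analysis window.
4. Cross-refer to SAP 5.2 so that the two rules agree, and check that the table shells match.
5. Keep population N for adverse-event incidence, any-time laboratory counts and the PHQ-9 summaries of subjects with at least one qualifying score or answer.

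The cost is a few lines of SAP text and a change of denominator in programming, with no new data. Denominators will vary by visit. An assessed denominator does not correct for informative dropout, but printing the number assessed makes the loss visible.
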